### **Blood pressure threshold**

We adopt a common BP target based on the recommendation of the latest hypertension guideline for uAOBP and home BP. Usually, central BP is lower than brachial BP. However, central BP device can be further classified into two types according to whether there is a preserved BP amplification, ie. Devices purports to

give an estimate of central BP relative to measured brachial BP (type I) or purports to estimate the intra-arterial central BP (type II). We previously conducted a hypertension prevalence survey in the 2013–2016 National Nutrition and Health Survey in Taiwan. In this national representative cohort, a type 2 central BP device is adopted to measure central BP. As shown in this study, comparable values of central and brachial SBP/DBP were noted. We therefore decided to use the same BP target for central BP monitoring to guide hypertension treatment.

## **Conclusion**

The GYMNs trial is ongoing now and due to complete in 2020. The trial should be fully powered to test its primary hypotheses. It is the first robust RCT to evaluate the optimal guiding strategy for hypertension will help define which BP monitoring is the most effective strategy to guide the clinical management of hypertension. Whatever the outcome, the findings of GYMNs are likely to influence future international guidelines for the choice of BP monitoring strategy in routine clinical practice in the care of hypertensive subjects.

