## Introduction

Throughout middle and old age, blood pressure (BP) is strongly and directly related to vascular and all-cause mortality, and lowering high BP has been shown to associate with a substantial risk reduction of cardiovascular diseases. However, the traditional BP used for clinical practice, the office BP, is usually measured in a busy and hurry clinical environment, and interfered by the well-known confounding whitecoat effect. As such, unattended automated office BP monitoring (AOBP) has been proposed as an effective solution and further promoted by Canadian physicians. Nonetheless, out-of-office BP, home BP and ambulatory BP, remains the methodology of recommendation for the detection of whitecoat effect, and its prognostic value has been demonstrated to be superior to the traditional office BP. In previous systematic review and meta-analysis, home BP has been shown to be as good as ambulatory BP in predicting target organ damage and a better guiding strategy than conventional office BP. Home BP monitoring, with its ability to detect morning and masked hypertension and a better tolerability than ambulatory BP monitoring for long-term use, can therefore be considered as a strategy of choice to replace office BP monitoring for guiding hypertension management.

Moreover, BP measurements in the peripheral arteries cannot serve as direct substitutes for their central counterparts because of the long-recognized differences

of blood pressure (BP) waveforms  and values  between the central aorta and peripheral arterial system. Thus, if the decisions on medication adjustment are made solely based brachial BP, there could be a considerable risk of over- or undertreatment.

Considering that there are many better strategies for guiding hypertension management than traditional office BP, there is an apparent need for investigating their comparative effectiveness and safety in the management of hypertension. We hypothesized that home BP may be non-inferior to AOBP and central BP-guided intervention in reducing ambulatory BP and designed the present randomized controlled trial.

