### **Study protocol**

Patients will be randomized to have hypertension management decisions made on the basis of the uAOBP, home BP, and central BP monitoring. Randomization will be done by using computer-generated randomization codes in 2 strata with baseline systolic BP (uAOBP) 130-155 mmHg and 155-180 mmHg. The BP measurements on left or right arm will also be determined by randomization codes.

To guide the management of hypertensive patients, medication adjustment will be made based on a published guideline with the measured BP through different BP monitoring methodologies. The use of different devices to obtain BP for guiding the care of hypertensive patients is aimed to determine whether these BP monitoring may be of comparable clinical value in routine practice. To achieve this, intervention patients will have medications titrated to normalize these different BP values. The target BP level, SBP 130 mmHg, of these different BP monitoring strategies are based on the latest guideline.

An overview of study protocol and acquired measures is presented in Table 1.

Although we encourage the adjustment of medication being adhered to the practice guideline, the choice of drug adjustment will be left to the discretion of the patient's attending doctor. During the measurement periods of home BP monitoring, no medication adjustment is allowable to preserve the comparability between different BP values. On the scheduled visits, the corresponding BP will be measured before meeting doctors and provided for clinicians to adjust patients' medication according to practice guideline. In summary, if the measured SBP is well within the target BP without possible side effects caused by antihypertensive agents, no medication adjustment is required. If the differences between measured SBP and target BP is less than 20 mmHg, the suggested maximal dose adjustment is 1 drug. If the BP differences are above 20 and 40 mmHg, addition of 2 drugs (or single pill combination) or 3 drugs (or single pill combination) are suggested, respectively. If low BP (less than 90/70mmHg) or any possible drug related side effects was noted, cautious adjustment of antihypertensive will be done. The dose adjustment and any possible side effects will be recorded throughout the whole study conduct period.

A sub-study will be performed to test the level of agreement between different measured BP values.

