### **Data Analysis and Statistical Analyses**

Based on data from our previous work, sample size (84 participants per group)

was determined on the basis of noninferiority between 3 independent groups ( $\alpha=0.05$ ;  $\beta=0.20$ ; standard deviation of ambulatory BP 11 mmHg; mean difference and non-inferior margin 5 mmHg, drop rate 10%).

We will test the normality of all parameters using the Shapiro–Wilk test. Categorical data are shown as proportions. Continuous data as means and standard deviations (SD) or as medium and interquartile ranges will be presented when appropriate.

Data will be analyzed on all patients who received the allocated strategy by intention-to-treat analysis if possible. For continuous variables of LV mass index, 24-hour ambulatory BP, heart rate, and quality of life, analysis will be undertaken using linear regression, with the dependent variable calculated as change over time. We will analyze DDD medication data recorded at all visits by using mixed regression models to account for repeated measures on individuals over time, with outcome variables log-transformed to correct heteroskedasticity where necessary.

The back-transformed means and confidence intervals are presented. Recommendations on medication use at each visit were categorized as maintain, increase, decrease or cease. A log-multinomial regression model will be used to assess the group differences for each of these 3 arms, with clustering on individuals to account for repeated measures over time.  $\chi^2$  test will be used to determine the

relationship between categorical variables. Intra-class correlations and paired t-test are used to assess the agreements between different strategies. A data safety monitoring board will be convened to oversee the progress of the study conduct and data relating to safety issue.

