## **Discussion**

### **Rationale**

The BP measurement is the clinical procedure of greatest importance given it serves as an imperative foundation in the management of hypertension, which is the most significant cardiovascular risk factor across the globe. However, a substantial whitecoat effect, the difference between office and out-of-office BP, can be observed in the measurement process of office BP in routine clinical practice, which can make the adjustment of antihypertensive agents a challenging task. Subsequently, home BP and uAOBP have been confirmed as successful strategies to eliminate the whitecoat effects. In addition, central BP has been shown to better conventional office BP in the prediction of cardiovascular risk and may be a more cost-effective strategy in the diagnosis of hypertension. In the era of evidence-based medicine, clinical trials are required to investigate the comparative effectiveness between these readily available BP monitoring strategies to inform clinical practice decisions. Using the gold standard of BP monitoring, the ambulatory BP, as the primary endpoint, we suggest home BP monitoring may be non-inferior to uAOBP and central BP monitoring as a guiding tool in the management of hypertension. Home BP is obtained by consecutive measurements and therefore is associated with a better accuracy and prognostic value than

conventional office BP. Moreover, home BP monitoring can be conducted in an easier way than uAOBP. If a comparable effectiveness could be demonstrated, it may have the potential to become the standard guiding procedure for hypertension.

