### **Double blind versus open label design for the treatment strategies**

We designed this study as a double-blind study for the clinical information will be provided for clinicians without the knowledge of the BP monitoring used for measure subjects' BP. The allocation concealment and blinding to patients, care givers, and outcome assessors will be rigorously kept avoiding possible placebo or performance bias. To our knowledge, it may be the first randomized controlled trial using the double-blind technique to evaluate the best BP monitoring strategy.

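### The plan announces conclusions about comparable value and the most effective strategy, but pre-specifies no test or error control for either; the only stated hypothesis is non-inferiority of home BP

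*Combined protocol and SAP*

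**What the plan says.** The combined protocol and SAP uses three kinds of claim.

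- **Non-inferiority of home BP.** Introduction: "We hypothesized that home BP may be non-inferior to AOBP and central BP-guided intervention in reducing ambulatory BP". The Rationale repeats it: "we suggest home BP monitoring may be non-inferior to uAOBP and central BP monitoring as a guiding tool".
- **Comparability of the methods.** Study protocol: the use of different devices is "aimed to determine whether these BP monitoring may be of comparable clinical value in routine practice".
- **Ranking.** Conclusion: the trial "will help define which BP monitoring is the most effective strategy to guide the clinical management of hypertension". The section on double-blind versus open-label design speaks of using the "double-blind technique to evaluate the best BP monitoring strategy".

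Under Data Analysis and Statistical Analyses, the sample size of 84 per group "was determined on the basis of noninferiority between 3 independent groups", with "standard deviation of ambulatory BP 11 mmHg" and "mean difference and non-inferior margin 5 mmHg". The same section analyses 24-hour ambulatory BP by linear regression on change. It does not say how an interval is compared with the margin, whether superiority is tested after non-inferiority, what would count as comparable, or how several pairwise comparisons are handled.

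**The concern.** These claims need different evidence. Non-inferiority shows only that home BP is not worse than a comparator by 5 mmHg or more. Comparability needs both ends of the interval inside the margin. Calling one strategy best needs superiority over the other two. The uAOBP versus central BP contrast, which any full ranking needs, is covered by no hypothesis.

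Without a fixed rule, one set of intervals could be reported after the fact as non-inferior, comparable or best, with no control of the error of whichever claim is chosen. Equally, if home BP really were better, no pre-specified route would let the sponsor say so. The Conclusion expects the findings to influence guidelines whatever the result, so the choice of claim matters.

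**Working it through.** **Inputs** (Data Analysis and Statistical Analyses): alpha 0.05 (sidedness not stated), power 80%, SD 11 mmHg, margin 5 mmHg, dropout 10%. **Assumptions:** true difference 0 for non-inferiority and equivalence; the SD given for ambulatory BP also applies to the change.

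**1. The plan's own figure.** n = 2 × [11 × (1.960 + 0.842) / 5]² = 76 evaluable per arm at one-sided 0.025. With dropout, 76 × 1.10 = 84, as stated (76 / 0.90 gives 85). One-sided 0.05 gives 60, or 66 to 67 with dropout, and does not fit. Bonferroni for two comparisons gives 93, and for three 102, before dropout; neither fits. A two-sided 0.05 superiority test of a 5 mmHg difference in one pair also gives 76, then 84 to 85.

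**2. Standard error of a pairwise difference.** 11 × √(2/76) = 1.784, so 5 / 1.784 = 2.802.

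**3. One pair.**
- Non-inferiority: Φ(2.802 − 1.960) = 80%.
- Equivalence, 95% interval within ±5: 2Φ(2.802 − 1.960) − 1 = 60%. With a 90% interval: 2Φ(2.802 − 1.645) − 1 = 75%.
- Superiority, unadjusted two-sided 0.05: 80% at 5 mmHg; Φ(3/1.784 − 1.960) = 39% at 3 mmHg. With Bonferroni for three pairs (critical value 2.394): 66% and 24%.

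**4. Several pairs.** The pairs share arms, so these come from simulating three independent arm means (1,000,000 draws, 76 per arm).

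| Claim | Probability |
|---|---|
| Home BP non-inferior to both (true difference 0) | about 69% |
| Home BP equivalent to both, 95% intervals | about 39% |
| Home BP equivalent to both, 90% intervals | about 60% |
| All three pairs equivalent, 95% intervals | about 32% |
| An arm best by 5 mmHg beats both others | about 69% |
| An arm best by 3 mmHg beats both others | about 23% |

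**5. Sensitivity to the assumed true difference.** If home BP is truly worse by 1 mmHg, one-pair non-inferiority power is Φ(4/1.784 − 1.960) = 61%. If it is truly better by 1 mmHg, it is Φ(6/1.784 − 1.960) = 92%.

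**6. Size for equivalence.** 80% power for one pair with a 95% interval needs 2 × [11 × (1.960 + 1.282) / 5]² = 102 evaluable per arm (114 enrolled, from 102 / 0.90). With a 90% interval it needs 83 (93 enrolled).

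**The case against.** Four arguments limit the point.

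- **Availability.** A reader might infer that neither wider conclusion can be reached in this trial. The documents do not support that. Superiority and equivalence can both be read from the same intervals once a rule is set. What is missing is the rule.
- **Sizing.** A reader might also infer that the trial was sized only for one-directional non-inferiority of home BP. The sample-size statement refers to three groups and names neither a direction nor home BP. The same 84 also fits a two-sided superiority test at 5 mmHg. That fit is for a single unadjusted pair, however, not a three-way ranking.
- **Status of the text.** The Conclusion says only that the trial will help define the strategy, and the mention of the best strategy sits in a discussion of blinding. Neither is a formal objective. This stands, and it lowers the weight of those passages. It does not remove the aim in the Study protocol section, which is not discussion text.
- **Meaning of comparable.** In the Rationale, the reference to comparable effectiveness follows the non-inferiority statement and may simply mean non-inferiority. The Study protocol wording, which covers all the methods, is the better ground for a two-sided reading, though no formal equivalence objective is stated there either.

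The 60% for equivalence depends on using a 95% interval; a 90% interval gives 75%. Both are shown above for that reason.

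**Conclusion.** The mismatch is real. The aim and the Conclusion announce claims for which the analysis section fixes no test and no error control. The defect is lack of pre-specification, together with modest power for some of the claims. It is not that the claims are out of reach.

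The nominal 80% applies to non-inferiority in one pair. Requiring it against both comparators, as the hypothesis reads, leaves about 69%. The Conclusion's statement that the trial should be fully powered concerns its primary hypotheses and cannot be extended to comparability against both (about 39% with 95% intervals). Nor can it be extended to ranking when the true advantage is 3 mmHg (about 23%). These figures rest on 76 evaluable per arm, SD 11 mmHg for the change, and a true difference of 0 where stated. This should be corrected, but it does not undermine the non-inferiority comparison.

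**What to change.** Before any unblinded comparison (the Conclusion says the trial is under way), add a claim rule to Data Analysis and Statistical Analyses. It uses the two-sided 95% interval for home BP minus each comparator in 3-month change in 24-hour SBP, where positive values mean home BP is worse.

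1. **Non-inferior:** upper limit below 5 mmHg against both comparators. Because both are required, no alpha adjustment is needed.
2. **Superior, only after step 1:** upper limit below 0 for that comparator. Claim best or most effective only if this holds against both. The plan should also say how superiority over just one comparator is treated. Two chances at one-sided 0.025 bound the error at 2 × 0.025 = 0.05, so either require 0.025 / 2 = 0.0125 when only one succeeds (Hochberg) or report it as descriptive.
3. **Comparable within 5 mmHg:** both limits within ±5, against both comparators. Report the direction whenever an interval excludes 0. A superiority result takes precedence in the wording.
4. **Worse:** a lower limit above 0 is reported as home BP worse, and above 5 as inferior beyond the margin. This is reported even when step 1 or 3 is also met.
5. **Anything else:** inconclusive.

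Report uAOBP versus central BP as an estimate with its interval, since no hypothesis covers it. Under this rule only home BP can be declared best, and comparability of all three methods is not a confirmatory claim. Reword the aim in Study protocol and the claim in the Conclusion accordingly, and state the two-comparator power.

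**Cost:** protocol and SAP wording only, with no new patients, visits or data. The headline claim becomes more modest. A sponsor wanting a confirmatory equivalence claim at 80% power would need more patients, as step 6 of the working shows.

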## **Acknowledgments**

This work was supported, in part, by grants from the Ministry of Health and Welfare (MOHW107-TDU-B-211-123001).

## **Conflict of interest disclosures:**

Microlife Co., Ltd., and National Yang-Ming University have signed a contract for transfer of the noninvasive central blood pressure technique. The contract of technology transfer includes research funding for conducting studies validating this technique.

**Table 1 Study plan**

Visit number	Screening	Visit 1	Visit 2	Visit 3	Visit 4	Visit 5	Visit 6	Visit 7
Day	-1~14	0	30 ( $\pm 7$ )	60 ( $\pm 7$ )	90 ( $\pm 7$ )	180 ( $\pm 7$ )	270 ( $\pm 7$ )	360 ( $\pm 7$ )
Visit timing			1M	2M	3M	6M	9M	12M
Site visits	√	√	√	√	√	√	√	√
Sign Informed Consent Form	√							
Medical history	√							
Inclusion/Exclusion Criteria	√	√						
Randomization		√						
Concomitant antihypertensive drugs	√	√	√	√	√	√	√	√
Medical record	√	√	√	√	√	√	√	√
Adverse Event (related study)		√	√	√	√	√	√	√
Height	√							
Weight	√	√	√	√	√	√	√	√
Physical examination	√	√	√	√	√	√	√	√
echocardiography		√						√
Blood test	√							√
Hemodynamic examination		√						√
ABPM		√			√			√
uAOBP	√	√	√	√	√	√	√	√
Home BP		√	√	√	√	√	√	√
Central BP		√	√	√	√	√	√	√
Questionnaire		√						√

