### **Randomization, Outcomes, and Masking**

Each patient will be randomly assigned, using a standard computer protocol at the General Clinical Research Center, Taipei Veterans General Hospital, Taipei, Taiwan, to intervention in a 1:1:1 ratio using sealed opaque envelopes (sequentially numbered). The study coordinator will oversee the enrollment and intervention assignment and keep allocation concealment. The Primary outcome is the change of 24 hour mean ambulatory SBP at 3 months. The secondary outcomes include the change of 24 hour mean ambulatory DBP at 3 months, decrease of left ventricular mass at 12 months, change of SBP/DBP measured by uAOBP monitoring, home BP monitoring, or central BP monitoring, change of quality of Life, change of medication count and side effects. Any possible treatment related side effects including hypotension, injurious fall, dizziness, electrolyte imbalance (serum Na <130meq/L, serum K > 5.5 or <3.0 meq/L), syncope, acute renal failure (increase in serum

creatinine > 1.5 times baseline, or increase in serum creatinine by  $\geq 0.3$  mg/dL), and bradycardia (heart rate <50 bpm detected by electrocardiogram) will be recorded and evaluated. The medication quantity will be determined by daily defined dose (DDD) calculated as per World Health Organization standard (the DDD is a system for exact quantification of drug amount and standardization to enable comparison across drug classes, eg,  $1 \times \text{DDD} = 150$  mg irbesartan or 5 mg amlodipine). The quality of life is assessed by the Bulpitt hypertension- specific questionnaire. Two-dimensional echocardiography will be obtained by Artida Echocardiograph (Toshiba Medical Systems Corporation, Tokyo, Japan) and end-diastolic left ventricular (LV) dimensions were used to calculate LV mass by an anatomically validated formula, and subsequently normalized body height The caring physicians will remain blinded to the allocation by providing them with the measured BP values through a standardized report form without the knowledge of the used BP monitoring devices. Except patient reported outcome and adverse events, the investigators and participants are blinded to all the above outcome variables (which will be calculated at the end of the study), and assessment of LV mass will be conducted on side-by-side images by a technician blinded to allocation.

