### **Data Safety Monitoring**

We have established a Data Safety Monitoring Board (DSMB) to monitor all aspects of the study. All issues related to participants' safety will be reported by the Medical Safety Officer to the independent DSMB, which will monitor data and oversee participant safety and will meet twice a year to monitor safety. They will also advise the research steering committee the study progress and performance, and make recommendations regarding the study continuation and protocol change. Efforts to early identify any major adverse outcomes of therapy will be made by the DSMB. The following is the possible safety events relating to the intervention: Serum sodium  $\leq$ 132 or  $>$ 150 mEq/L; serum potassium  $<$ 3.0 or  $>$ 5.5 mEq/L; serum creatinine increase by at least 50% to a value  $\geq$ 1.5 mg/dL since the last study lab; heart rate  $<$ 40; ECG complete heart block, or bradycardia  $<$ 40 beats/min; injurious falls; syncope; any unexpected events for which the investigator believes that could be attributed to the intervention strategies. Serious adverse events are any adverse events that meet any of the following criteria: fatal or life-threatening, result in

significant or persistent disability, require or prolong hospitalization, and any events that investigators judge to represent significant hazards or harm to research.

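### The sections on adverse events conflict over whether events judged unrelated are recorded, so serious and listed events may be filtered by attribution before arms are compared

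*Combined protocol and SAP*

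**What the plan says.** Five places in the combined protocol and SAP bear on which events are recorded.

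- **Table 1 Study plan.** The only adverse-event row reads "Adverse Event (related study" and is ticked from Visit 1 (randomisation) to Visit 7. There is no separate row for serious events.
- **Study protocol.** "The dose adjustment and any possible side effects will be recorded throughout the whole study conduct period".
- **Randomization, Outcomes, and Masking.** The safety part of the secondary outcomes is "Any possible treatment related side effects including hypotension, injurious fall, dizziness, electrolyte imbalance", followed by syncope, acute renal failure and bradycardia.
- **Data Safety Monitoring, event list.** The list opens with "The following is the possible safety events relating to the intervention". It names laboratory and ECG thresholds, injurious falls and syncope, and closes with "any unexpected events for which the investigator believes that could be attributed to the intervention strategies".
- **Data Safety Monitoring, serious events.** "Serious adverse events are any adverse events that meet any of the following criteria: fatal or life-threatening". Persistent disability and events that "require or prolong hospitalization" are among the further criteria. None requires a causal link.

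Safety is a comparative question in the Abstract, the Introduction and two Discussion sections (the challenges of office BP, and uAOBP). The Introduction also says that if decisions rest on brachial BP alone, "there could be a considerable risk of over- or undertreatment".

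**The concern.** A relatedness condition applied before recording differs from one applied at analysis, because an event that was never written down cannot be recovered. Three features make this matter here.

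First, the intervention is a BP value on a standardised report, and the treating physician is meant not to know its source. That physician can judge whether a drug might have caused an event. Whether the monitoring strategy led to it is much harder to judge.

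Second, the named events are drug effects or signs of excessive lowering. No list names a harm of undertreatment, such as a cardiovascular admission, and such an event does not fit naturally under treatment-related side effects. It reaches the data only through the serious-event definition.

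Third, the trial is small for safety, so each lost event costs a good deal of information.

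**Working it through.** **1. The sections side by side**

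| Place | Events covered | Tied to relatedness? |
|---|---|---|
| Table 1, adverse-event row | Adverse events, Visits 1 to 7 | Yes, by its label |
| Study protocol | Side effects, whole study | Loosely (possible side effects) |
| Randomization, Outcomes, and Masking | Safety secondary outcome | Yes, though possible relatedness suffices |
| Data Safety Monitoring, listed events | Laboratory, ECG, injurious falls, syncope | By the opening line only; no test for each event |
| Data Safety Monitoring, unlisted events | Unexpected events | Yes, by investigator belief |
| Data Safety Monitoring, serious events | Fatal, life-threatening, disabling, hospitalised and similar | No |

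**2. Two events traced through the text**

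- *A stroke admission judged unrelated.* The Table 1 label does not call for it, and it is not a listed side effect. It is a serious adverse event by the Data Safety Monitoring definition.
- *An injurious fall, without admission, judged unrelated.* The Table 1 label does not call for it, and the outcome wording covers it only if it is possibly treatment-related. The Data Safety Monitoring section lists it outright.

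For both, the answer depends on which section the site follows. No sentence tells sites to record serious events regardless of attribution. The Data Analysis and Statistical Analyses section has a general provision for χ² tests on categorical variables but names no comparison of serious events by arm.

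**3. The plan's own figure**

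The plan gives 84 per arm (252 in all) from an SD of 11 mmHg, a margin of 5 mmHg, 80% power and 10% dropout. With one-sided alpha 0.025 and a true difference of zero:

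n = 2 × (1.960 + 0.842)² × 11² / 5² ≈ 76 per arm.

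Allowing for dropout, 76 × 1.10 = 83.6, or 84, and 76 / 0.90 = 84.4, or 85. The figure reproduces. It was set for ambulatory systolic BP, not for safety events.

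**4. What filtering could cost**

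The documents give no event rates, so the risks p and the recorded fraction q are assumptions. Expected recorded events per arm are 84 × p × q, and the chance of none in an arm is (1 − pq)^84.

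| Assumed 12-month risk p | Expected, all recorded (q = 1) | Expected, half recorded (q = 0.5) | Chance of none, q = 1 | Chance of none, q = 0.5 |
|---|---|---|---|---|
| 2% | 1.68 | 0.84 | 18% | 43% |
| 5% | 4.20 | 2.10 | 1% | 12% |
| 10% | 8.40 | 4.20 | under 0.1% | 1% |

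If q is the same in every arm, the expected ratio between arms is unchanged and only precision is lost. If q differs, the expected ratio of recorded counts is multiplied by q₁/q₂. The documents give no value for either fraction, so neither the direction nor the size of a bias can be stated.

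**5. Could q differ by arm?**

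The stated masking of physicians works against it. However, the BP monitoring section provides a home device to patients allocated to the home arm and gives clinicians morning and afternoon averages, which could reveal the arm. Equal filtering is plausible but not assured.

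**The case against.** The strongest reply is that the safety section already captures what matters. Its serious-event definition has no causality condition, so a fatal or hospitalised stroke qualifies. Falls, syncope and the laboratory and ECG thresholds are listed without an event-by-event attribution test. All participant-safety issues are to go to the DSMB. The Table 1 label is terse and may be no more than awkward English, and the word possible sets a lower bar than judged related. A medical-record row and a physical examination are also scheduled at every visit.

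Much of this stands, and it rules out several stronger readings that a reader might infer:

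- *That serious events will go uncounted, or that the DSMB will not see them.* The documents support only that they may be missed by a site working from Table 1.
- *That undertreatment harms are almost never recorded.* The serious ones meet the definition. Undertreatment is also measured directly in all arms by ambulatory BP at 3 and 12 months.
- *That lost events bias the non-inferiority conclusion.* Non-inferiority is specified for ambulatory BP; no non-inferiority test of safety is planned.
- *That the Introduction treats undertreatment as a general hazard of every strategy.* The sentence concerns decisions based on brachial BP alone, although brachial values do guide two of the three arms.

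The reply does not remove the conflict. A definition of seriousness is not an instruction to collect, and only events that sites record can be forwarded to the DSMB. The medical-record row is not defined as a route for events.

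**Conclusion.** The point holds as an inconsistency with a practical consequence. Table 1, the outcome text and the catch-all for unlisted events tie recording to relatedness; the serious-event definition does not. A site could follow Table 1 in good faith and leave out a serious or listed event that it considers unrelated, and that judgement would rest with clinicians masked to the strategy.

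The likely cost is lost information on a stated aim. Halving the recorded events halves the expected count per arm: 1.7 to 0.8 at an assumed 2% risk, 8.4 to 4.2 at 10%. These figures rest on assumed risks, an assumed recorded fraction of one half, and all 84 patients followed for 12 months. A difference in filtering between arms is possible, but the documents do not allow it to be quantified. The primary outcome is not affected. This is a worthwhile, inexpensive correction and does not make the design unsound.

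**What to change.** Reconcile the three places so that they give one rule.

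1. **Table 1.** Reword the adverse-event row to cover all serious adverse events and all listed events of interest, regardless of relationship, from randomisation to Visit 7.
2. **Randomization, Outcomes, and Masking, and Data Safety Monitoring.** State the same rule. Say which events count as listed, since the two lists differ (sodium and heart-rate thresholds, for example, are not the same in both).
3. **Case report form.** Record the investigator's causality opinion as a separate field that does not decide whether an event is entered.
4. **Data Analysis and Statistical Analyses.** State that serious and listed events of any cause are reported by arm and to the DSMB, with events judged related as a supporting listing.

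Collecting every non-serious, unlisted event is optional; limiting that collection is a defensible choice if it is stated.

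The cost is protocol and form wording, plus somewhat more data entry at visits already scheduled. No extra visit or test is needed.
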